#### 3 BACKGROUND AND STUDY OBJECTIVES

## 3.1 Background

The prevalence of atopic eczema (syn. 'atopic dermatitis', 'eczema') has increased 2–3 fold during the last century, affecting up to 20% of children and 4-7% of adults in European countries (1, 2). Severe cases of atopic eczema can have a major impact on health-related QoL of patients and their families. Approximately 85% of cases begin in early childhood and up to 30% of early atopic eczema cases persist into adulthood. Atopic eczema has a strong and clinically relevant association with a range of inflammatory co-morbidities, in particular airway disease (asthma, hay fever), food allergies, atopic eye disease, clinical depression and attention-deficit hyperactivity disorder (3).

Atopic eczema is multifaceted and regulated by a complex array of genetic and environmental factors that lead to epidermal-barrier dysfunction and inappropriate up-regulation in pro-inflammatory immune responses (4, 5). There is increasing recognition that atopic eczema is a highly complex syndrome with multiple causes and mechanistic pathways that clinically can be distinguished by age of onset, severity of illness, ethnic modifiers, response to therapy, and extrinsic flare factors (e.g. infections, stress) (6). The search for objective molecular and laboratory disease severity and prognostic markers is still in its infancy but is essential to inform a personalised therapeutic approach.

Most children and adults with atopic eczema can be treated efficiently with emollients and topical antiinflammatory agents. However, around 5% of patients require systemic immuno-modulatory therapies to induce disease remission and long-term control (7). Ciclosporin (CsA) is currently the only treatment approved in Europe, and only in adults (8). Its long-term use is limited due to the risk of renal toxicity. Alternative systemic immuno-modulatory therapies include methotrexate (MTX) and azathioprine (AZA) (2). Biologic treatments are also being actively researched in early phase trials (e.g. dupilumab and lebrikizumab), and dupilumab has now entered clinical practice, with others expected to enter clinical practice in a couple of years.

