#### 5 STUDY DESIGN

This is an observational register study of adult and paediatric patients with atopic eczema requiring systemic immune-modulatory therapy, either conventional systemic immuno-suppressive treatments (excluding oral corticosteroids) or a novel biologic or small molecule treatment.

Dupilumab has recently received approval from the EMA and FDA and other biologics and small molecules are being tested in clinical trials.

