#### 9 STATISTICAL CONSIDERATIONS

## 9.1 Primary endpoints

Change in disease severity between baseline and three months into treatment (V3), comparing the different treatment modalities with each other, using the EASI (Eczema Area and Severity Index).

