## 9.3 Sample size calculation

#### Treatment effectiveness:

Based on the results of the paediatric and adult severe AE treatment surveys we conducted in the UK [24], we expected that at least 200 patients on conventional systemic treatments needed to be recruited within 2 years and followed up for at least 12 months; 40% (80) of patients are expected to be on azathioprine, 35% (70) of ciclosporin, and 24% (50) on methotrexate. This takes a 10% loss to follow up into account. Should the pharmaceutical industry decide to support the A-STAR project financially, then we hope to be able to collect one year follow up data on patients on dupilumab during the life-time of this award.

Under these patient number assumptions, all comparisons of the EASI score (azathioprine vs ciclosporin, azathioprine vs methotrexate, ciclosporin vs methotrexate and dupilumab vs each of the other drugs) are able to detect differences that are below the published minimal clinically important difference (MCID) for each drug with high power (95%) [25]. Differences that can be detected are shown below alongside the MCIDs. Hence, with the projected patient numbers we will be able to detect differences between groups that are clinically meaningful.

	EASI score					
Comparison	Difference detectable with 95% power and expected sample sizes	Comparison	Difference detectable with 95% power and expected sample sizes	MCID		
AZA vs CsA	3.5	AZA vs Dup	3.2	6.6		
AZA vs MTX	3.9	MTX vs Dup	3.7	6.6		
CsA vs MTX	4.0	CsA vs Dup	3.3	6.6		

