#### Treatment safety (pharmacovigilance):

Although we will not have adequate statistical power for a comparative analysis of rare and long-term latent adverse events of the different agents within the confines of this three-year project due to the relatively small patient numbers and short follow-up period, we will still be able to conduct a meaningful descriptive analysis of more common adverse events collected over an at least one-year period for each treatment modality.

The initial analyses will consist of comparisons in baseline status between the individuals in the treatment cohorts. For the purposes of analysis (initially) follow-up time will be censored in both cohorts if there is switching to another class of biologic therapy and censored in the standard therapy group if there is switching to a biologic agent. The adverse events of interest are calculated per person time of follow-up, after the start of therapy.

Sample size of the novel biologics/small molecule exposure group will be largely determined by external factors, including:

- 1) NICE technology assessments and resulting recommendations;
- 2) whether NICE indicates the need for pharmacovigilance and recommends patients are registered in our registry;
- 3) funding of by NHS, and
- 4) uptake by prescribing dermatologists.

The size of the comparison cohort will be more under our control. However, it is difficult to anticipate the magnitude of rate differences for adverse events between the cohorts as patients from all groups are likely to have had prior exposure to immunosuppressive drugs.

Assuming i) the risk of adverse event is proportional to the length of exposure with equal risk per year (note this may not be so), ii) power of 80%, and iii) a significance level of 5%, the following applies:

Annual adverse	Rate ratio	Person years exposure
event rate		per group
1/10,000	2	235,508
1/1000	2	23,590
2/1000	2	11,817
1/100	2	2,321
2/100	2	1,146
4/100	2	551
5/100	2	437
10/100	2	201

For guidance, the estimated risk of certain adverse events are as follows:

Squamous cell carcinoma with ciclosporin use 1 in 320 Non-melanoma skin cancer 1 in 1,000 Melanoma in high dose PUVA (phototherapy) 1 in 1,666 Melanoma in normal person 1 in 10,000

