## 9.4 Statistical analyses

#### Treatment effectiveness:

Descriptive statistics, t-tests, regression and Kaplan-Meier survival analyses will be applied as appropriate to examine treatment effectiveness between drugs, adverse events, drug cost/QALY, and drug survival respectively. Primary treatment effectiveness variables are the mean EASI score, corrected for baseline scores. We will also compare the proportion of patients with an EASI reduction of 50%. For the purposes of analysis, follow up time will be censored in both cohorts if there is switching to another class of therapy and censored in the standard therapy cohort if there is switching to another systemic agent.

The potential effect of *FLG* genotype on treatment response:

In addition to the above analyses, we will conduct a subgroup analysis to investigate whether *FLG* genotype stratifies with treatment response, as *FLG* genotype is potentially an important biomarker but has not been investigated in the context of conventional systemic therapy for atopic eczema. We hypothesise that those with one or more *FLG* loss-of-function mutation(s) respond less well to therapy, as has been seen for the biologic treatment omalizumab [26]. Based on the available literature for patients with moderate-to-severe atopic eczema, we expect 40% of our participants to carry one or more *FLG* loss-of-function mutations. Under these assumptions, all treatment comparisons (AZA vs CsA, AZA vs MTX, CsA vs MTX, dupilumab vs any of the standard systemic medications) are able to detect an effect size as low as 20% difference in treatment responses that are close to the expected MCID\* (=MCID x 80%) with 80% power. Further detail on the differences that can be detected are shown below alongside the expected MCIDs (MCID\*).

The following assumptions are made in these calculations:

- -Available sample sizes are Azathioprine (AZA): 32, Ciclosporin (CsA): 28, Methotrexate (MTX): 20, Dupilumab (Dup): 40 (expecting 40% of our study participants to carry a *FLG* mutation).
- -MCID and corresponding standard deviation is for children and adults combined and reduced by 20% to 5.3.
- -The analysis will use a 2-sample t-test to look at change in score (for the purposes of checking the sample size). The actual analysis will test interactions and therefore have lower statistical power.
- -A 5% significance level (2-sided) will be used.

	EASI score			
Comparison	Difference	Comparison	Difference	MCID*

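### Section 9.4 censors effectiveness follow-up by different switch rules in the two cohorts, although the planned comparisons are between named drugs

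*Protocol*

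**What the plan says.** Section 9.4 (Treatment effectiveness) has two censoring triggers. The first applies to everyone: "follow up time will be censored in both cohorts if there is switching to another class of therapy". The second applies to one side only: follow-up is "censored in the standard therapy cohort if there is switching to another systemic agent".

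The two cohorts come from section 5, which admits patients on "either conventional systemic immuno-suppressive treatments (excluding oral corticosteroids) or a novel biologic or small molecule treatment". No section defines class.

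The comparisons are at drug level. Section 9.1 sets the primary endpoint as EASI change to V3, "comparing the different treatment modalities with each other". Section 9.2 adds EASI change to six and twelve months by treatment group. Section 9.3 gives detectable differences for "azathioprine vs ciclosporin, azathioprine vs methotrexate, ciclosporin vs methotrexate and dupilumab vs each of the other drugs". The *FLG* table in section 9.4 uses the same pairs.

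More than one biologic is foreseen: section 3.1 names dupilumab and lebrikizumab, and section 9.4 sets a long-term recruitment target for each biologic separately.

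**The concern.** A comparison of dupilumab with, say, methotrexate asks how patients do on each drug. That needs one rule, applied to both sides, for when a patient stops contributing to the index drug. Section 9.4 is stricter for the conventional side: any change of systemic agent ends follow-up there, while on the biologic side only a change of class does. Time on a second biologic of the same class can therefore remain in follow-up that began with the first, and time on a second conventional drug cannot.

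At stake is whether the 6- and 12-month EASI contrasts compare like with like. This is not a detail left to an analysis plan. The protocol states the rule, so an analysis plan that followed it would inherit the mismatch, and one that corrected it would depart from the protocol.

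**Working it through.** **Step 1: apply the section 9.4 triggers to each kind of switch.**

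| Change of drug | Cohort at the time | Follow-up censored? |
|---|---|---|
| Conventional to another conventional | Standard | Yes, by the second trigger |
| Conventional to biologic | Standard | Yes |
| Biologic to conventional | Biologic/small molecule | Yes, as a class change on any ordinary reading |
| Biologic to biologic, different class | Biologic/small molecule | Yes, by the first trigger |
| Biologic to biologic, same class | Biologic/small molecule | **No** |

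The first and last rows are the equivalent events on the two sides, and they are treated differently. How often the last row occurs depends on what class means. If all biologics form one class, every biologic-to-biologic switch stays uncensored. If class means mechanism, only same-mechanism switches do. The safety text in section 9.3 hints at the narrower reading, since there follow-up is "censored in both cohorts if there is switching to another class of biologic therapy".

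**Step 2: look for text elsewhere that repairs the mismatch.**

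- Section 7.2 (Baseline 2, 3, 4) gives any switch to a new systemic agent a fresh baseline and a restarted visit schedule, in every group. This governs data collection. It lets an analyst separate the episodes, but section 9.4 does not say to do so.
- Section 9.4 (Adverse events) apportions time when two biologics have been used, but only for risk of adverse events.
- The safety rule in section 9.3 puts its extra standard-group trigger elsewhere: "censored in the standard therapy group if there is switching to a biologic agent". It does not supply a common rule.

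**Step 3: scale.** No figure in the protocol depends on this rule. The only yardstick is the section 9.3 table, where the three dupilumab comparisons have detectable EASI differences of 3.2, 3.3 and 3.7. These are coherent. With 80 patients on azathioprine and 100 on dupilumab (inferred from 40 being 40% in section 9.4), the implied SD is 3.2 / [(1.960 + 1.645) × √(1/80 + 1/100)] = 3.2 / (3.605 × 0.15) = 5.92. All six comparisons give 5.87 to 6.00.

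**Step 4: what the unequal rule can do to a 12-month mean.** All inputs here are assumptions. Let a share p of a group fail the index drug and switch. Had they stayed on it, their EASI would be d points above that of the patients who stay. Let a second drug lower it by g. Relative to everyone remaining on the index drug:

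- Biologic side, switchers kept in: the mean is lowered by p_B × g.
- Standard side, switchers censored and simply absent: the mean is lowered by p_S × d.
- Net shift in favour of the biologic = p_B × g − p_S × d.

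Take p from 5% to 15% and d and g from 8 to 14 points. Each side is then flattered by 0.05 × 8 = 0.4 up to 0.15 × 14 = 2.1 points. The net runs from 0.4 − 2.1 = −1.7 to 2.1 − 0.4 = +1.7. If p is the same on both sides and g = d, the net is zero.

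If the last pre-switch value were instead carried forward on the standard side, that side would not be flattered, and the net would be p_B × g, that is 0.4 to 2.1 in favour of the biologic. A wider assumed range for the biologic side alone (2-20% switching, 3.3-10 points) gives 0.02 × 3.3 = 0.07 up to 0.20 × 10 = 2.0 points. The sign and size turn on inputs that the protocol does not contain.

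**The case against.** The strongest reply is that the uneven wording has not been shown to harm the comparison, and much of this reply stands.

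- **Direction.** A reader might infer that the rule favours biologics by construction, because their failures can be rescued within counted follow-up. The documents do not support this. Censoring the failures on the standard side removes them from the later mean and can flatter that side as much or more.
- **Attribution.** A reader might infer that a second biologic's results are credited to the first. Section 9.4 leaves that follow-up uncensored but names no drug to which it belongs. Under section 7.2 the later visits are timed from the new baseline, so an analyst could well assign them correctly.
- **Drug survival.** A reader might infer that survival on the first biologic is overstated by the share who switch within class. The protocol summary in section 2 describes drug survival by time to discontinuation of treatment, and leaving one drug for another is ordinarily a discontinuation whatever the class.
- **Oral corticosteroids.** A reader might infer that replacing the index drug with oral corticosteroids triggers censoring only in the standard cohort. Replacing a biologic with them would plausibly be a change of class, which already applies to both cohorts. Section 7.5.1 treats rescue use as additional medication to be recorded.
- **Reach.** Comparisons among azathioprine, ciclosporin and methotrexate share one rule and are unaffected. Few patients are likely to have switched by V3.

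What the reply does not remove is the stated difference between the two cohorts, the absence of a definition of class, and the lack of any link from section 9.4 to the new-baseline rule.

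**Conclusion.** The point holds as a mismatch between a stated censoring rule and the comparisons it serves. For dupilumab against a conventional drug, a switch within the conventional group ends follow-up, while a switch to a second biologic of the same class does not. The 6- and 12-month EASI comparisons are mainly exposed; the V3 primary endpoint is probably little affected.

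No net bias in either direction is established. The figures above, from 1.7 points against the biologic to 2.1 in its favour beside detectable differences of 3.2 to 3.7, rest on assumed switch shares and EASI differences and on the assumed handling of censored data. They show that the effect need not be negligible, not that it has a given sign. The conclusion assumes that the standard therapy cohort means patients on conventional systemics and that some biologics in use will share a class. It should be corrected because the rule as written does not give like-for-like comparisons and the correction is cheap.

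**What to change.** Replace the censoring sentence in section 9.4 (Treatment effectiveness) with one rule for every group, for example: *For comparisons between named drugs, follow-up on the index drug ends at a switch to any other systemic immuno-modulatory agent, within or between classes, and is handled identically in all treatment groups; data after the new baseline (section 7.2) belong to the new treatment episode.*

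Reserve class-level follow-up for analyses labelled as class comparisons, and define class there.

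The cost is one sentence plus a definition, and slightly less follow-up attributed to the first biologic. Visits, data collection and clinical care do not change, because section 7.2 already re-baselines every such switch. The change makes the two sides follow the same rule. It does not make censoring at a switch uninformative, so the handling of the censored data still has to be specified, in the same way for all groups.

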#### Adverse events/pharmacovigilance:

Drug adverse events are calculated per person time of follow up, after the start of therapy. Time-dependent regression analyses will be undertaken to compare event rates between groups, using standard multivariable analyses to reduce confounding. We will explore the use of other statistical techniques, including propensity score matching, to accommodate confounding by indication. As children and adolescents may have a different phenotype of atopic eczema compared to adults and may respond differently to systemic therapy, we will explore this further in comparative analyses.

Estimating the risk of rare adverse effects with a smaller signal, especially lymphoma will be facilitated by long-term linkage to the national cancer registry (in addition to the control group). The risk window for cancer being defined as once exposed always at risk. Where two biologicals have been used, the proportion of time spent on each will define its possible contribution to risk. Where the adverse event is rare or where a biological intervention is under-represented in the register, the numbers of patient's data can also potentially be increased by sharing data with other compatible registers such as those operating in Germany, Italy, Spain, France, Denmark, and the Netherlands.

The aim in the long-term is to recruit at least 4,000 patients on conventional treatments and also at least 2,000 on each biological intervention (depending on the uptake of these drugs in clinical practice). 4,000 patients in

each cohort, biologicals and conventional treatment would give an exposure of 12,000 patient years in each group. This would give power to detect at least a 3- or 4-fold increase in risk of events occurring at a frequency of 1 in a 1000 or 1 in 2000 patients. Rarer events would be detected if the relative risks were higher.

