- b Full blood count, renal and liver function are recommended at all study visits. Other bloods to be done according to local practice (e.g. Hep B, Hep C and HIV). An additional blood sample at week 1 for patients in MTX may be collected according to local practice.
- c After 12 months of participation, questionnaires to be done every 6 months regardless of treatment.
- d For subjects with a diagnosis of asthma of  $\geq$  12 years old.
- e Can be collected at any time during the study.
- f Timepoints are subject to change if decided by the Study Steering Committee.
- g For patients participating in the bioresource, severity assessments (EASI, IGA, POEM, itch severity and A-STAR Bioresource CRF) need to be performed on the same day as the collection of biomaterial.
- h To be conducted as close to the baseline visit/assessments as possible, in particular for participants consenting to the collection of biomaterial for mechanistic studies. For patients only participating in the observational aspects of the study therapy needs to start within a maximum of 28 days following the baseline assessment.

\*\*\* If patient switches their main systemic treatment or restarts the same systemic treatment after a decision for discontinuation by the treating physician has been made (excluding short-term breaks in treatment), Baseline 2 (or if applicable: Baseline 3, 4 etc.) assessments will be performed and then further visits will continue as per original schedule (D1, W4, W16, 6M, etc.).

- i For patients participating in the bioresource, the visit 2 window is +/- 1 week.
- j For patients participating in the bioresource, the visit 3 window is +/- 1 week with +/- 2 weeks in exceptional circumstances.

Participants will be followed up for as long as possible until withdrawal.

While on systemic therapy, follow up is three-monthly after the first 4 weeks up to Visit 6 (12 months). Then follow up will be every six months (for example: Visit 7 will be at 18 months, Visit 8 will be at 24 months and so on).

Once off systemic treatment, patients will be seen every six months.

Patients will be followed up for as long as possible, even if they stop treatment.

The following target visit windows apply: V2 +/-2 weeks (i.e. weeks 2-6), and then +/-4 weeks thereafter (i.e. V3 weeks 12-20 etc.).

EASI - Eczema Area Severity Index
IGA - Investigator Global Assessment
POEM - Patient Oriented Eczema Measure

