#### Baseline 2 (Baseline 3, Baseline 4, etc.) - If switching/restarting systemic treatment

If during participation in the study a patient starts a new systemic immuno-modulatory agent or restarts the same systemic treatment after a decision for discontinuation by the treating physician has been made (excluding short-term breaks in treatment), the patient will have a further 'Baseline' visit and retake all baseline assessments, with exception of family and personal medical history and collection of blood for genetic analyses. Baseline Adverse Events information will also be collected. A new signed Informed Consent will not be required but confirmation of continued consent should be documented in the medical notes. Following this new baseline, visits will be scheduled as per original schedule (Day 1, Week 4, Week 16, and so on). If a patient has simply started on a second systemic agent alongside another, then no baseline visit is required, just 3-monthly visits as per protocol.

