## 7.3 Follow up visits

Follow up visits will occur at 4 weeks after the start of systemic immuno-modulatory therapy, 16 weeks and three-monthly thereafter whilst on systemic therapy up to Visit 6 (12 months). Then follow up visits will be every six months (for example: Visit 7 will be at 18 months, Visit 8 will be at 24 months and so on). Once treatment has been stopped, follow ups are also done six-monthly.

If a patient is recruited within the first 2 weeks after treatment initiation, visit 2 will happen at week 4 (±2 weeks), as per usual schedule of events. In situations when patient recruitment occurs 3-4 weeks after treatment initiation, visit 2 assessments will be conducted on the day of recruitment.

Follow up visit procedures:

a. Confirm informed consent status.

- b. Review of co-morbidities and concomitant medication.
- c. Review of systemic therapy (any changes since last visit/current dose) and disease control (number of controlled weeks).
- d. If treatment has been switched: reasons for switching, and outcomes in patients at the point at which the subsequent treatment is initiated.
- e. Reasons if discontinuing (lack of effectiveness, adverse events, patient preference, disease remission, other).
- f. Smoking and alcohol consumption.
- g. Review of adverse events experienced since the previous visit.
- h. Any A&E, hospital, GP or healthcare skin-related visits, and whether due to disease exacerbations, including skin infection.
- i. Days lost from usual activities due to skin disease (e.g. school, work).
- j. Any further phototherapy (TL01, PUVA or other; number of doses).
- k. Physical exam (at the discretion of the treating physician and with their oversight), including weight, and BP.
- I. Safety blood samples are recommended at all study visits.
- m. EASI, -IGA, POEM, itch severity (NRS), IDQOL/CDLQI/DLQI, EQ-5D-5L (adults)/EQ-5D-Y (4-16 years' old), and RECAP.
- n. Completion of ACT in subjects with diagnosed asthma of ≥ 12 years' old\*.
- o. Optional: collection of blood samples, skin biopsies (≥16 years of age), and skin tape strips for mechanistic work and collection of skin microbiome/metabolite samples, using standardised operation procedures across all study participating centres that have the expertise and facilities to take part on this module.\*\*
- \*ACT only done at 16 weeks and 12 months and then every six months.
- \*\*Only done at 4 and 16 weeks, as well as, one year into treatment.

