# 10.7 Reporting procedures

All adverse events should be recorded from initiation of treatment until withdrawn from study. Depending on the nature of the event the reporting procedures below should be followed. Any questions concerning adverse

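### Adverse event rates per person-time pool on-drug and off-drug periods with different visit frequency, which can distort comparisons of non-serious and laboratory events between drugs

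*Protocol*

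**What the plan says.** **Collection.** At each follow-up visit the site carries out a "Review of adverse events experienced since the previous visit" (Protocol Section 7.3; Section 8.2 says the same). Section 10.7 sets the recording period: "All adverse events should be recorded from initiation of treatment until withdrawn from study". Laboratory, physiological and examination abnormalities that need intervention or further investigation count as adverse events (Section 10.2.1). Safety bloods and physical examination are tied to study visits (Section 2 schedule notes; Section 8.2).

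**Visit frequency.** Section 7.3: "Follow up visits will occur at 4 weeks after the start of systemic immuno-modulatory therapy, 16 weeks and three-monthly thereafter whilst on systemic therapy". This pattern ends at month 12. For later visits on treatment the section says: "Then follow up visits will be every six months (for example: Visit 7 will be at 18 months". For patients who come off their drug it says: "Once treatment has been stopped, follow ups are also done six-monthly". After a switch or restart, Section 7.2 (Baseline 2) returns the patient to the dense schedule: "Following this new baseline, visits will be scheduled as per original schedule (Day 1, Week 4, Week 16, and so on". A second agent added to an existing one brings no new baseline, only 3-monthly visits.

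**Analysis.** Sections 9.3 and 9.4 define the rate over follow-up time after the start of therapy: "Drug adverse events are calculated per person time of follow up, after the start of therapy". Section 9.3 names certain switches as censoring events but not stopping. Section 9.4 compares groups by time-dependent regression with multivariable adjustment and will explore propensity score matching. It mentions neither visit frequency nor time since start of the current drug. Comparing adverse event profiles between treatment groups is secondary endpoint 4 (Section 9.2).

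**The concern.** The numerator depends on how often a patient is asked and tested, and that frequency changes with time on the drug. The denominator gives every month of follow-up the same weight. The named adjustments concern who receives a drug, not how closely the patient is observed afterwards.

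The mix of early, late and off-drug time will differ between drugs. A newly launched drug has mostly first-year time. An established drug with long-stayers has mostly six-monthly time. A drug that is stopped and not replaced contributes off-drug time at six-monthly visits. Two drugs with the same true rate could then show different recorded rates, and secondary endpoint 4 would read this as a difference in safety. Section 9.3 says that the initial three-year project can support only descriptive analysis of the more common adverse events. Those are largely the events exposed to this problem.

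**Working it through.** **1. The protocol's own figure.** The only calculation for adverse event rates is the Section 9.3 table of person-years needed to detect a rate ratio of 2 (80% power, 5% level). The usual two-proportion formula, two-sided and without continuity correction, is

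n = [1.96·√(2p̄(1−p̄)) + 0.842·√(p₁(1−p₁) + p₂(1−p₂))]² / (p₂−p₁)², with p₂ = 2p₁.

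It gives 235,430 at 1/10,000 (protocol 235,508), 23,511 at 1/1000 (23,590), 2,319 at 1/100 (2,321) and 199 at 10/100 (201). The table reproduces closely. It assumes equal risk per year, which the protocol itself says may not hold, and it does not deal with ascertainment.

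**2. Visit intervals (Sections 2 and 7.3).** Visits at weeks 4, 16, 26, 39 and 52 give year-1 intervals of 4, 12, 10, 13 and 13 weeks (sum 52). Later intervals are 26 weeks. That is 5 visits in year 1 and 2 a year afterwards. The mean time from an event to the visit that asks about it, ΣL²/(2ΣL), is 1.3 months in year 1 and 3.0 months later.

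**3. Events that must be recalled.** Assumption, not in the protocol: the chance that an event is still reported decays at rate λ per month. The share captured over intervals L is Σ[(1−e^(−λL))/λ] / ΣL. Year-1 intervals in months are 0.92, 2.76, 2.32, 3 and 3; later ones are 6. True rates are equal throughout. Three years is the follow-up implied by Section 9.4 (12,000 patient-years / 4,000 patients).

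| λ per month | Year 1 captured | Later captured | Year 1 / later | 1-year drug / 3-year drug | Switched at 16 weeks / 3-year drug | Stopped at 16 weeks, no switch, 3 years counted / 3-year drug |
|---|---|---|---|---|---|---|
| 0 | 1.000 | 1.000 | 1.00 | 1.00 | 1.00 | 1.00 |
| 0.05 | 0.937 | 0.864 | 1.08 | 1.05 | 1.06 | 0.99 |
| 0.10 | 0.879 | 0.752 | 1.17 | 1.11 | 1.13 | 0.98 |
| 0.20 | 0.777 | 0.582 | 1.34 | 1.20 | 1.24 | 0.96 |
| 0.40 | 0.621 | 0.379 | 1.64 | 1.35 | 1.44 | 0.93 |

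The switched column assumes that follow-up is censored at the switch. The last column uses intervals of 0.92 and 2.76 months, five of 6 months and one of 2.32 months.

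In terms of a recall half-life of 26, 13 or 8 weeks, the year-1 / later ratio is 0.862/0.721 = 1.19, 0.749/0.541 = 1.39 and 0.637/0.397 = 1.60.

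**4. Abnormalities seen only at visits.** Assumption: a silent abnormality lasts D weeks and is found only if a visit falls within that time. The share detected is Σmin(D, L)/ΣL. No recall loss is involved.

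| D (weeks) | Year 1 | Later | Ratio |
|---|---|---|---|
| 4 | 20/52 = 0.385 | 4/26 = 0.154 | 2.50 |
| 8 | 36/52 = 0.692 | 8/26 = 0.308 | 2.25 |
| 13 | 52/52 = 1.000 | 13/26 = 0.500 | 2.00 |
| 20 | 1.000 | 20/26 = 0.769 | 1.30 |
| 26 | 1.000 | 1.000 | 1.00 |

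The ceiling of 2.5 is the ratio of visit counts, 5/2. Testing between visits would lower these ratios.

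**5. Effect of banding.** Within a band of on-drug time where both drugs follow the same schedule, the captured share is the same for both, so it cancels and the ratio returns to 1.00.

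**The case against.** Three stronger readings are tempting, and the protocol does not support them.

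- A reader might infer that the schedule biases the rates by construction. It does not. Each look-back covers the whole interval and Section 10.7 leaves no period unrecorded. With complete recall the ratio for symptomatic events is 1.00. Bias requires capture to worsen over longer intervals, or an abnormality that comes and goes between tests.
- A reader might infer that any drug with short use looks less safe. That holds when short use ends in a censoring switch or when follow-up is recent. A drug that is simply stopped moves to six-monthly visits at once, and its off-drug time stays in the denominator. The artefact then reverses slightly (0.99 to 0.93). Section 3.1 says that long-term ciclosporin use is limited, but not whether patients then switch or stop.
- A reader might infer that drugs will be compared only on a crude pooled rate. Section 9.4 also plans time-dependent regression. With its origin at the start of the current drug, that would already compare like with like. The choice may be made in a statistical analysis plan that is not shown.

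Other routes of capture also count: unscheduled visits (Section 7.3.1), bloods taken at GP practices with results passed on (Section 8.2), and linkage to hospital, primary care, mortality and cancer data (Section 12.5). Linkage will not happen immediately, but Section 12.5 gives missed events as a reason for it. These routes protect serious events, deaths and cancers well, and minor or laboratory events less.

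Bands of time since start are not a complete answer either. Add-on drugs are seen 3-monthly, and patients who stop early are seen six-monthly within their first year, so neither group fits the bands.

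These objections narrow the point without removing it. The rate that the protocol does define mixes time observed at different intensity, and the named adjustments do not address this.

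**Conclusion.** The point holds in limited form, for non-serious events and chiefly for laboratory and examination abnormalities. The visit counts, the look-back method and the person-time denominator are all in the protocol. The loss of capture is an assumption, so the size is a range. Year 1 against later years gives 1.00 with complete look-back, about 1.1 to 1.6 at 5% to 40% loss per month, and at most 2.5 for short-lived abnormalities tested only at visits. A drug with one year per patient against one with three years gives 1.00 to 1.35 under the same recall losses.

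The direction depends on how exposure ends. A genuine early excess of events after starting a drug would produce the same crude pattern, and a pooled rate cannot tell the two apart. The change is worth making, but the point does not undermine the register's serious-event or cancer analyses.

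**What to change.** In Section 9.4, for non-serious and laboratory adverse events:

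- Report and compare rates within bands of on-drug time since start of the current drug that follow the visit schedule: 0 to 16 weeks, 16 weeks to 12 months, and after 12 months.
- Report time after stopping separately.
- Flag add-on periods, or stratify them by their actual visit schedule.
- State that the time-dependent regression uses time since start of the current drug as its time axis, or is stratified by these bands.

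Pooled rates may stay for serious events and linked outcomes.

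The cost is a few sentences and a band variable built from treatment dates and the recorded visit dates. No extra visits or data are needed. Intervals within each band will be somewhat wider. Banding keeps both denser visits and any early excess from being read as a difference between drugs, but rates compared across bands would still mix the two.
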